### 6.2.7 Exposure to Study Drug

Exposure to study drug will be calculated separately for SAD and MAD + MAD Extension parts.

**SAD part:** exposure will be set to 1 if subject was dosed.

**MAD + MAD Extension part:** date of last MAD dosing - date of first MAD dosing + 1.

The exposure calculation will not take into account breaks in therapy.

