1.3 Investigational Medicinal Product Background

Mutations in the *DNM2* gene or genes upstream of *DNM2* in the molecular pathway result in higher activity of DN2 protein (either by activation or higher accumulation of the protein), which in turn plays a critical role in manifestation of CNM of different types in pediatric and adult patients (Cowling et al., 2014; Cowling et al., 2017; Buono et al., 2018).

A summary of the experiments with DYN101 is provided below. For detailed information on DYN101, refer to the latest version of the Investigator's Brochure (IB) (Dynacure).

Compatibility of DYN101 200 mg/mL eq. sterile solution with the selected infusion solution and the selected infusion tubing for clinical study DYN101-C101, was evaluated in a compatibility study. The compatibility study mimicked the worst-case interaction of DYN101 200 mg/mL eq. sterile solution with tubing, infusion solution and infusion bag.

The compatibility study evaluated both the physico-chemical and chemical stability of DYN101 in the infusion solution after adding, after 6 hours and after 24 hours. Two infusion bags were prepared (3.5 mL DYN101 added to 250 mL sodium chloride 0,9%) and 20 mL samples were taken through the tubing at T0. The prepared infusion bags were stored at room temperature and at T6h (bag 1) and T24h (bag 2), a second 20 mL sample per bag is taken through the tubing. Test parameters were appearance, pH, viscosity, assay DYN101, chromatographic purity and osmolality, determined at time points 0, 6, and 24 hours.

No physico-chemical or chemical degradation was observed in any of the samples tested in the compatibility/stability study. Based on the test results obtained in the study, it can be concluded that the proposed study set-up, using 1-mL or 3-mL syringes with luer lock, together with 0.9% sodium chloride infusion bags and the proposed infusion tubing is compatible with the DYN101 solution.

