5.2 Dosage and Administration

The IMP will be prepared by the pharmacist or delegated qualified site personnel. The ideal body weight determined at SAD Day 1, MAD Week 1 Day 1, and MAD Week 13 will be used to calculate the applicable dose. In case the ideal body weight is higher than real body weight, real body weight will be used to calculate the applicable dose. Refer to the Pharmacy Manual for the exact calculations of the volume to be administered. The corresponding volume of IMP will be taken from the vial and diluted into a 0.9% sodium chloride solution (in an infusion bag), resulting in an IV solution with the respective concentration of the dose level. A substantial change (as judged by the investigator) in body weight will be reported as an AE, and it will be discussed with the sponsor whether the dose calculation should be adjusted.

Detailed instructions for aseptic preparation of the applicable doses and all items related to IMP administration will be described in the Pharmacy Manual.

The IMP will be dispensed IV using a validated infusion pump. Subjects will be dosed by qualified site personnel. A physician will be available on-site during infusions.

In each cohort, there will be an interval of at least 7 days between dose administration of the first and second subject in a cohort, irrespective of their sub-cohort. The 48-hour safety data from the first subject in a cohort will be reviewed by the medical monitor before the next subject can be dosed. In addition, any SAE data from the first subject received up until the moment of treatment of the second subject will be taken into account.

In the SAD part, subjects will receive a single IV administration of IMP over approximately 1 hour at a low (1.5 mg/kg), middle (4.5 mg/kg), or high (up to 9 mg/kg) dose level in Cohorts SAD1, SAD2, or SAD3, respectively (unless the IDMC advises otherwise).

In the MAD part, subjects will receive weekly IV administrations of IMP over approximately 1 hour for a period of 12 weeks, at the same or different dose level (low, middle, or high) as in their SAD cohort in Cohorts MAD1, MAD2, or MAD3, respectively (unless the IDMC advises otherwise).

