7.11.2 Individual Treatment Interruptions and Dose Adjustments

As thrombocytopenia is a known side effect of ASOs, it is important to always check that the subject has a normal platelet count before dosing. If a decreased platelet count is detected (i.e. value $<$ lower limit of normal [LLN]), a retest should be performed immediately in the local laboratory. If the retest confirms a platelet count value $<$ LLN, the subject may NOT be dosed.

Treatment interruptions will be considered in the event of any suspicion of vasculitis or in the event of any of the following situations that may occur, considered related to IMP:

- Platelet count is between 75,000 and 150,000/ μ L; in that case the subject can be dosed as soon as the platelet count has returned to a value $>$ LLN and dosing can resume at the same dose.
- Platelet count is $<$ 75,000/ μ L; in that case the subject can be dosed as soon as the platelet has returned to a value $>$ LLN, however dosing should be resumed at 50% of the previous dose.
- Platelet count is $<$ LLN and a previous dose interruption had taken place because of decreased platelet values; in this case, the medical monitor should be contacted to discuss possible additional treatment interruptions and/or dose adjustments.

Furthermore, treatment interruptions and/or dose adjustments for an individual subject should be considered in the event of any of the following events:

- Elevation of AST and/or ALT $>$ 3 \times ULN
- Elevation of bilirubin $>$ 2 \times ULN
- Elevation of ALP $>$ 1.5 \times ULN
- Elevation of ALT and/or AST in temporal association with nausea, vomiting, anorexia, abdominal pain, or fatigue
- Clinically significant deteriorating kidney function during treatment
- Any other clinically significant deterioration during treatment considered related to IMP.

In these instances, the medical monitor should be contacted to discuss potential treatment interruptions and/or dose adjustments.

In case a treatment interruption is needed for any safety reason for more than 4 consecutive weeks, or if there is a second treatment interruption on the initial or reduced dose level, the site should always contact the medical monitor to determine the best strategy for the subject, considering the individual risk-benefit ratio.

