## SAP Amendments before database lock

Version	Issue Date	Section	Revision/Addition	Rationale
0.1	12-SEP-2019			First draft for internal review
0.2	26-SEP-2019			Draft version for sponsor review
0.3	04-OCT-2019			Draft version for IDMC organizational meeting
0.4	14-NOV-2019			Version including updates based on comments.
1.0	16-DEC-2019			Version 1.0
2.0	29-SEP-2020	1  1, 6.4  6.13.5 6.14.2 - 6.14.6	Updated to the latest protocol amendment.  Added COVID-19 summaries.  Shift table to be presented from BL to the worst recorded result in each trial period (not by each visit).	To use the latest protocol amendment.  Requirement to report impact of COVID-19.  Shift table for each visit separately would get too big.
3.0	17-AUG-2022	1  4  5	Added note that only abbreviated CSR will be done due to study termination. Updated to the latest protocol and IDMC charter version.  Sample size updated.  Dosing information updated.	To get updated with latest document versions.  Updated per the latest protocol.  Updated per the latest protocol.

		6.2.6	Added details for partial date imputations.	Clarification for data derivation.
		6.2.13	Added information about the data collection.	General clarifications.
		6.4	Small clarifications in disposition section.	To update readability.
		6.10	Added summary of doses received.	New summary due to many interruptions.
		6.13.2, 6.13.3	Summary of categorical data using frequency tables not descriptive statistics.	To use better method summarizing data.
		6.13.4	Added collected data categories.	To help understand underlying data.
		6.13.5, 6.13.6	Clarified what will be reported for abbreviated CSR.	General clarification.
		6.14.2	Added data normalization for lab data.	To make lab parameters comparable across different labs.
		8	Updated primary analysis and final analysis section.	Updated to match the study termination.
		9	Updated IDMC analysis.	Per the latest IDMC charter.
		10	Added note for the changes from planned protocol analyses.	Updated to match the study termination.

---

		12	Removed tables that are not done for the abbreviated CSR.	Updated to match the study termination.
--	--	----	---	---

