### 6.2.8 Treatment Compliance

Treatment compliance is calculated by visit and overall for SAD part and MAD + MAD Extension parts.

Treatment compliance at each visit will be calculated as

$$100 \times \frac{\text{Actual volume administered (mL)}}{\text{Planned Total Volume (mL)}}$$

Overall treatment compliance for MAD + MAD Extension parts will be calculated as

$$100 \times \frac{\text{Sum of actual volume administered (mL)}}{\text{Sum of planned Total Volume (mL)}}$$

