### **6.10 Exposure to Study Drug**

Extent of exposure (number of days of exposure to study drug) will be presented by treatment group (cohort, subcohort) for the Safety Analysis Set and separately for SAD and MAD parts.

Additionally, number of doses will be summarized.

All dosing information will be listed.

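### No specified SAP summary reliably shows reduced doses: MAD duration ignores breaks, compliance is a volume ratio with an undefined denominator, and the dose count shows only missed infusions

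*SAP*

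**What the plan says.** **Duration.** SAP 6.2.7 sets MAD plus extension exposure to "date of last MAD dosing - date of first MAD dosing + 1" and adds: "The exposure calculation will not take into account breaks in therapy".

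**Compliance.** SAP 6.2.8 introduces its formula with "Overall treatment compliance for MAD + MAD Extension parts will be calculated as". The formula is 100 times the summed actual volume over the summed planned total volume, both in mL. A by-visit version has the same form.

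**Dose count.** SAP 6.10 says: "Additionally, number of doses will be summarized". The SAP change log gives the reason as "New summary due to many interruptions". It does not list 6.2.7 or 6.2.8 among the sections revised in version 3.0. Section 12 has no separately titled table for the count; it may sit in Table 14.1.5.1.

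**Holds and reductions.** Protocol 7.11.2 bars dosing when a retest confirms platelets below the lower limit of normal. In one platelet situation it says "dosing should be resumed at 50% of the previous dose". It also allows interruptions or dose adjustments for liver, kidney and other findings. Protocol 5.2 lets the IDMC change the dose of a cohort or sub-cohort.

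**Preparation.** Under Protocol 5.2 a volume of product is drawn from the vial and diluted in a bag, "resulting in an IV solution with the respective concentration of the dose level". The exact volume calculation is left to the Pharmacy Manual.

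**Use.** The primary endpoint compares adverse event frequency and severity by dose. SAP 6.3 labels the groups 1.5, 4.5 and 9 mg/kg only. Tables 14.1.5.1 (exposure) and 14.1.5.2 (compliance) are IDMC outputs, and SAP 8 carries the IDMC output set into the abbreviated CSR.

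**The concern.** In a dose-escalation trial, an adverse event rate at a labelled dose can be judged only against the dose subjects actually received. The protocol foresees that some subjects will skip infusions and that some will continue at a lower dose. The SAP's three exposure figures are a time span, a volume ratio and a count, and none is expressed in mg or mg/kg. If part of a cohort continues on less than its labelled dose, its event rate after the reduction belongs to a lower dose than the column heading states. The reader of the summary tables has no dependable way to see this. SAP 6.14 presents safety by treatment received, but gives no rule for placing a subject whose dose was reduced.

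**Working it through.** The documents state no exposure or compliance result, so there is no figure to reproduce. The check applies the SAP formulas to model courses.

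**Inputs.** There are 24 weekly infusions, 12 in the MAD part and 12 in the extension (Protocol 3.1.1). The formulas are those of SAP 6.2.7 and 6.2.8. The 50% step comes from Protocol 7.11.2. The timing of holds and reductions is assumed for illustration. One full dose counts as 1.

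**Duration.** Any course that starts at Week 1 and ends with the Week 24 infusion gives 23 × 7 + 1 = 162 days, whatever happens in between. A permanent stop after 12 doses gives 11 × 7 + 1 = 78 days, so duration does show permanent stops.

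**Courses.**
- H: held Weeks 9–12, otherwise full. Doses given: 20. Dose received: 20/24 = 83.3%.
- R: full to Week 12, then 50%, no missed visit. Doses given: 24. Dose received: (12 + 12 × 0.5)/24 = 18/24 = 75%.
- HR: 8 full, 4 held, 12 at 50%. Doses given: 20. Dose received: (8 + 6)/24 = 14/24 = 58.3%.

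**Compliance under each reading SAP 6.2.8 leaves open.** Bag volume is treated as constant.

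| Reading of volume and planned total | H | R | HR |
|---|---|---|---|
| Drug volume, plan kept at assigned dose, all scheduled visits | 20/24 = 83.3% | 18/24 = 75% | 14/24 = 58.3% |
| Drug volume, plan kept at assigned dose, dosed visits only | 20/20 = 100% | 18/24 = 75% | 14/20 = 70.0% |
| Drug volume, plan re-set at reduction, all scheduled visits | 20/24 = 83.3% | 18/18 = 100% | 14/18 = 77.8% |
| Bag volume, all scheduled visits | 20/24 = 83.3% | 24/24 = 100% | 20/24 = 83.3% |
| Plan re-set or bag volume, dosed visits only | 100% | 100% | 100% |

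Only the first row equals the dose received in all three courses. The SAP specifies neither that row nor any other.

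**Why the bag reading would hide a reduction (illustration only).** The compatibility study in Protocol 1.3 used a 200 mg/mL product, with "3.5 mL DYN101 added to 250 mL sodium chloride 0,9"% as the test mixture. At an assumed 70 kg, 9 mg/kg is 630 mg or 3.15 mL of drug, and half is 1.575 mL. Total volumes are 253.15 and 251.575 mL, a ratio of 99.4%. As drug volumes, the same two doses have a ratio of 50%. No passage makes 250 mL the clinical bag volume, so the conclusion does not rest on 99.4%.

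**The three figures together for course R:** 162 days, 24 doses, and 100% compliance if the plan is re-set or the bag volume is used. A full course gives the same three numbers.

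**The case against.** **The dose count exposes interruptions.** This stands. H and HR each show 20 doses, not 24. A reader might infer that an interrupted cohort will look fully dosed, but SAP 6.10 contradicts that. The gap is confined to reduced doses.

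**Compliance may work as intended.** This also stands in part. If volume means drug volume, the plan stays at the assigned dose and held visits count, the ratio shows both holds and reductions. It would be wrong to say that compliance cannot show them. The fault is that the SAP does not fix the reading.

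**Course R may be uncommon.** The platelet route to 50% will usually include a missed infusion, so the count would flag something. It would still understate the loss. With 11 full doses, one missed and 12 at 50%, the count is 23 of 24, while the dose received is (11 + 6)/24 = 70.8%. Adjustments for other findings, or by the IDMC, need no missed visit.

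**Subject-level data are listed.** Listings 16.2.5.1 and 16.2.5.2 cover dosing, compliance, interruptions and rate changes, and about 18 subjects can be read one by one. This limits the harm but does not supply a by-cohort summary. Protocol 9.6 promises the number of subjects receiving each dose at each time point. If that means dose level, the SAP has not carried it over, and SAP 10 does not declare the change.

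**Toxicity would still be reported.** Thrombocytopenia is an adverse event of special interest with its own table. Under Protocol 7.3, laboratory abnormalities that lead to interruption or modification are reported as events if they meet the definitions. The triggering events are therefore not hidden. What is missing is the dose behind the later event rates.

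**Two further inferences are unsupported.** The change log mentions many interruptions but gives no cause, and nothing shows that any 50% reduction occurred. Nor are all four IDMC reviews affected: MAD1 starts only after the second, so only the third and fourth can include MAD breaks.

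**Conclusion.** The point holds as a gap in exposure reporting. Duration cannot show a hold followed by resumption. Compliance is undefined exactly where the protocol foresees departures from the plan, and no specified summary gives mg/kg received, dose intensity or the number of reductions. In the model courses, a subject on 75% of the assigned dose can match a full course on all three planned figures. One on 58.3% can show compliance anywhere from 58.3% to 100%.

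These sizes assume 24 weekly doses, the last at Week 24, with hypothetical timing of holds and reductions. They show what the rules permit and do not estimate what happened. With the trial terminated, the consequence is mainly for reading adverse events by dose in the abbreviated CSR, and for any IDMC review that included MAD data.

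**What to change.** Keep duration in days and the number of doses. Replace the volume ratio in SAP 6.2.8 with relative dose intensity:

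100 × (sum of mg/kg actually infused) / (assigned cohort mg/kg × number of weekly infusions scheduled up to IMP discontinuation),

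counting a missed infusion as 0. The mg/kg infused is the prepared dose times the fraction infused, using the dosing weight of Protocol 5.2. State how an IDMC-directed change of cohort dose enters the denominator. For H, R and HR the measure gives 83.3%, 75% and 58.3%. Permanent stops remain visible in duration.

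Add to Tables 14.1.5.1 and 14.1.5.2, by cohort, the cumulative mg/kg and the numbers of subjects with at least one missed and at least one reduced dose. Confirm which table carries the dose count. If the volume ratio is also kept, define whether volume means drug or diluted infusion, and define planned volume for held visits and after a reduction.

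The cost is SAP wording, one re-derived variable and a less favourable compliance figure. Infusion information is entered in the eCRF and dispensing is documented in accountability records (Protocol 5.6), so no new collection should be needed. That assumes the prepared dose can be recovered from those records. No clinical dosing rule changes.

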### 6.2.8 Treatment Compliance

Treatment compliance is calculated by visit and overall for SAD part and MAD + MAD Extension parts.

Treatment compliance at each visit will be calculated as

$$100 \times \frac{\text{Actual volume administered (mL)}}{\text{Planned Total Volume (mL)}}$$

Overall treatment compliance for MAD + MAD Extension parts will be calculated as

$$100 \times \frac{\text{Sum of actual volume administered (mL)}}{\text{Sum of planned Total Volume (mL)}}$$

### 6.2.9 Inexact Values

In the case where a safety laboratory variable is recorded as “> x”, “≥ x”, “< x” or “≤ x”, a value of x will be taken for analysis purposes.

### 6.2.10 Electrocardiogram Data

For ECG data recorded on continuous scales, if more than one value is recorded at a time point, the mean value rounded to the integer will be presented. For overall interpretation if more than one value is recorded, the most severe (worst case) of the respective readings will be taken.

### 6.2.11 Unscheduled Visits

Only scheduled post-baseline laboratory and vital signs values will be tabulated. Post-baseline repeat/unscheduled assessments will be disregarded, although these post-baseline assessments will be listed in the relevant appendices to the CSR.

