Complement assessments ^{g)}					✓	✓		✓		✓		✓	
Coagulation assessments ^{h)}			✓		✓	✓	✓	✓	✓	✓	✓	✓	
Erythrocyte sedimentation rate ^{h)}			✓		✓	✓	✓	✓	✓	✓	✓	✓	
Urinalysis (dipstick)					✓	✓		✓		✓		✓	
Urine pregnancy test ⁱ⁾						✓		✓		✓		✓	
Collect AEs/SAEs	✓	✓	✓		✓	✓	✓	✓	✓	✓	✓	✓	✓

	SAD FOLLOW-UP and WASHOUT												
Trial Period	Single Dose Follow-up and Washout Periods ^{a),b)}												
Time Point: Week (W)	SAD W1		SAD W2		SAD W3	SAD W5	SAD W7	SAD W9	SAD W11	SAD W13	SAD W15	SAD W17	Phone call ^{c)}
Time Point: Day (D)	D2	D3	D8	D11	D15	D29	D43	D57	D71	D85	D99	D113	Every 2 weeks after W17
Time Window			±1d	±1d	±3d	±3d	±3d	±3d	±3d	±3d	±3d	±3d	±3d
Timing Relative to Baseline	+24h	+48h	+7d	+10d	+2w	+4w	+6w	+8w	+10w	+12w	+14w	+16w	
PK Assessments													
Blood sample for PK ^{j)}	✓	✓	✓		✓	✓		✓		✓		✓	
PD/Exploratory Efficacy Assessments													
CGI-I and PGI-C questionnaires					✓								
Respiratory function					✓								

AE: adverse event; BP: blood pressure; CGI-I: Clinical Global Impression of Improvement; EoT: End of Treatment; FU: follow-up; IPF: immature platelet fraction; IV: intravenous; MFM: Motor Function Measure; PD: pharmacodynamics; PGI-C: Patient Global Impression of Change; PK: pharmacokinetics; RR: respiratory rate; SAD: single ascending dose; SAE: serious adverse event.

Due to restrictions imposed in response to a pandemic that restrict subject visits, please contact the medical monitor to determine strategy for continuing the subject in the trial. All efforts must be employed to maintain subject safety. Assessments, if feasible, must be collected during a phone call with the subject. The site should arrange the collection of the blood and urine samples, if at all possible.

- Assessments of a single visit can be split over 2 consecutive days, if required.
- Where possible, the visits as of Day 8 will take place on the same day of the week as the baseline visit (Day 1).
- Subjects will be contacted by phone by qualified site personnel every 2 weeks following Week 17, to follow-up on concomitant medications and AEs, until their assigned MAD cohort has been opened.
- Symptom-directed physical examination. A neurologic assessment is also to be performed at Week 17.

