- Where possible, the visits in the MAD part will take place on the same day of the week as Day 1 (and of the SAD part, if applicable). A window of ±3 days is allowed for visits as of Week 3, with a minimum of 4 days between 2 subsequent infusions. Assessments of a single visit can be split over 2 consecutive days, if required.
- Replacement subjects starting in the MAD part should sign an ICF for participation in the MAD part, and their eligibility will be assessed (see Trial Schedule for the Screening Period) before the first IMP administration in the MAD part (MAD Week 1 Day 1). If needed (to be discussed with the sponsor), these subjects will have a run-in period before they can start in the MAD part (see Trial Schedule for Run-in Period). A DNA sample (optional) and a muscle biopsy should be taken before the first IMP administration. If needed, replacement subjects in MAD1 and MAD2 may have the second muscle biopsy taken after 6 to 12 weeks of MAD treatment, after discussion with the sponsor.
- All assessments need to be done pre-dose.
- Slow infusion over 1 hour; subjects will be monitored on site by qualified site personnel for a minimum of 1 hour after the infusion for safety. Platelet counts as determined by the local laboratory need to be within normal ranges before IMP administration.

- e) A symptom-directed physical examination (and measurement of body weight at MAD Week 1 Day 1) will be performed.
- f) During an unscheduled visit which will occur between 6 weeks and 7 days prior to the baseline visit for subjects for whom the last visit in the SAD part will be more than 3 months before the baseline visit in the MAD part.
- g) To be performed pre-dose.
- h) Only applicable if a liver ultrasound and/or hepatic elastography was not performed during the screening period.

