6. TRIAL SCHEDULE AND ASSESSMENTS

6.1 Trial Schedule

Refer to the [TRIAL SCHEDULES](#) for an overview of the frequency and timing and sequence of the trial measurements and procedures. Further details will be described in the site manuals (e.g. Laboratory Manual, Site Operations Manual).

Repeat or unscheduled samples may be taken for safety reasons or for technical issues with the samples.

For subjects suffering from an intercurrent illness (e.g. viral or bacterial infection) that could interfere with the PD/exploratory efficacy assessments (see Section [6.2.4](#)), these assessments should be postponed for at least a week until the subject has recovered.

Subjects will be confined to the clinic for at least 7 hours after SAD dosing, the first dosing or a change of dosing) during MAD, for at least 4 hours during all other clinic visits during MAD, and may be confined to the clinic for any 24-hour urine collection. Additionally, the subject may be confined to the clinic for their convenience if assessments will be performed on consecutive days.

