6.1.3.3 Multiple Ascending Dose Part

For subjects for whom the last visit in the SAD part was more than 3 months before the baseline visit in the MAD part, there will be an unscheduled visit (physical examination and clinical laboratory parameters) which will occur between 6 weeks and 7 days prior to the MAD baseline visit. Liver ultrasound and hepatic elastography have to be performed before the baseline visit in the MAD part. The first IMP administration in the MAD part cannot be started before the liver ultrasound and hepatic elastography results are available.

Subjects will receive weekly IV administrations of DYN101 for a period of 12 weeks, i.e. from MAD Week 1 to Week 12.

Replacement of withdrawn subjects can occur under the circumstances described in Section 3.1.2. New subjects who did not participate in the SAD part should sign an ICF for participation in the MAD part, and the eligibility will be assessed (see Section 6.1.1) before the first IMP administration in the MAD part (MAD Week 1 Day 1). Replacement subjects may or may not need a run-in period, in consultation with the sponsor (see Section 6.1.2). A DNA sample (optional) and a muscle biopsy should be taken before the first IMP administration.

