### **6.14.2 Laboratory Data**

Descriptive statistics (n, mean, SD, median, min, max) of the observed values and change from baseline (continuous data) will be presented by treatment group (cohort, subcohort) and visit for each hematology, chemistry and urinalysis parameter.

Each measurement (continuous data) will be classed as below, within, or above normal range, based on ranges supplied by the laboratory used. Shift tables in relation to the normal range from baseline to the worst recorded result in each trial period will be presented.

In addition to central laboratory, platelet counts will be analyzed in local laboratory. This local laboratory data will be reported as part of the laboratory tables describe above.

All laboratory data will be listed.

Some laboratory samples are analyzed in local laboratory instead of central laboratory. If data from same sample is available from both central and local laboratory then the records from central laboratory will be used. Local laboratory might use different units and/or normal ranges to central laboratory and this need to be taken into account as described below.

For shift tables (low/normal/high) local lab data will use the original units and normal ranges.

For descriptive statistics, local laboratory results are normalized using location-scale normalization or scale normalization to be comparable to central lab results. These methods are described by Karvanen (2003).

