### 6.14.3 Coagulation Data

Descriptive statistics (n, mean, SD, median, min, max) of the observed values and change from baseline (continuous data) will be presented by treatment group (cohort, subcohort) and visit for each parameter.

Shift tables in relation to the normality (Normal, Abnormal NCS, and Abnormal CS) from baseline to the worst recorded result in each trial period will be presented.

All data, including details of any abnormalities, will be listed.

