### 6.14.4 Complement Data

Descriptive statistics (n, mean, SD, median, min, max) of the observed values and change from baseline (continuous data) will be presented by treatment group (cohort, subcohort) and visit for each parameter.

Each measurement (continuous data) will be classed as below, within, or above normal range, based on ranges supplied by the laboratory used. Shift tables in relation to the normal range from baseline to the worst recorded result in each trial period will be presented.

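### Laboratory shift tables promise the worst recorded result while SAP 6.2.11 discards unscheduled values, and the protocol's CTCAE v5 abnormality counts are dropped without being declared

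*SAP*

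**What the plan says.** **Which values are tabulated.** SAP 6.2.11 tabulates only scheduled post-baseline laboratory and vital signs values. It continues: "Post-baseline repeat/unscheduled assessments will be disregarded, although these post-baseline assessments will be listed in the relevant appendices to the CSR".

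**What the shift tables show.** For hematology and chemistry, SAP 6.14.2 plans shifts "from baseline to the worst recorded result in each trial period will be presented". SAP 6.14.3 plans the same for coagulation on a three-level scale: "Shift tables in relation to the normality (Normal, Abnormal NCS, and Abnormal CS) from baseline to the worst recorded result". SAP 6.14.4 does so for complement: "Shift tables in relation to the normal range from baseline to the worst recorded result in each trial period will be presented". None of these sections mentions scheduled visits or 6.2.11.

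**Baseline.** SAP 6.2.3 sets one baseline for the whole trial, the last value before the first SAD dose. That value may itself be scheduled, unscheduled or a repeat.

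**Off-schedule sampling.** Protocol 6.1 provides for it: "Repeat or unscheduled samples may be taken for safety reasons or for technical issues with the samples".

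**Laboratory abnormalities.** Protocol 9.8 plans the number and percentage of subjects with laboratory abnormalities at each scheduled time point. They are determined by CTCAE version 5, and laboratory normal ranges are used only where no grading exists. SAP 6.14.2 classes values as below, within or above the normal range and applies no grade. SAP Section 1 says that all protocol-planned analyses are included in the SAP, Section 8 says that the full safety analyses are kept despite termination, and Section 10 lists the changes from the protocol.

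**The concern.** The two SAP rules select different data for the same four tables. If 6.2.11 governs, the tables do not show the worst recorded result. If 6.14.2 to 6.14.4 govern, 6.2.11 is breached. SAP Section 12 validates these tables by independent programming, so two programmers could each follow the SAP and produce different tables.

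The selection is also lopsided: an unscheduled abnormal value can set the baseline but cannot register as a shift after dosing.

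The CTCAE point is separate. A safety summary planned in the protocol is missing from a SAP that describes itself as complete, and the section reserved for such changes does not mention it.

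Safety is the primary objective of this first-in-human trial, and dose levels will be compared in these summary tables. Listings show individual values but give no counts by dose.

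**Working it through.** The documents state no figure that bears on this point, so there is none to reproduce. The check compares the texts, counts the schedule and the output list, and scales the effect of one subject.

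**1. Can the rules be reconciled?** Only by reading worst recorded as worst scheduled. A subject with normal scheduled values and one abnormal unscheduled value in a period then appears as unshifted. A retest that merely confirms an abnormal scheduled value moves no low/normal/high cell. On the coagulation scale, a retest could still move a subject from Abnormal NCS to Abnormal CS.

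**2. Are off-schedule laboratory results foreseen?** Yes, in three ways.

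- *Between SAD Week 17 and MAD Week 1.* There are 0 scheduled laboratory visits, only calls: "Subjects will be contacted by phone by qualified site personnel every 2 weeks following Week 17".
- *Before MAD baseline.* If the last SAD visit was more than 3 months earlier, protocol 6.1.3.3 requires a laboratory visit that it calls unscheduled. Note f of the MAD Part schedule gives the timing: "During an unscheduled visit which will occur between 6 weeks and 7 days prior to the baseline visit". Six rows carry note f: platelets, clinical laboratory, cardiac troponin, complement, coagulation and ESR. Because SAP baseline precedes the SAD dose, these planned results are post-baseline and fall under the exclusion in 6.2.11.
- *During MAD Weeks 1 to 25.* Dosing is weekly, but the laboratory schedule is sparser in places:

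| Panel | Weeks 1–12 | Weeks 13–25 | Total | Weeks without |
|---|---|---|---|---|
| Hematology, chemistry, coagulation | 12 of 12 | 7 of 13 (13, 15, 17, 19, 21, 23, 25) | 19 of 25 | 6 |
| Complement | 4 of 12 (1, 3, 5, 9) | 4 of 13 (13, 17, 21, 25) | 8 of 25 | 17 (17/25 = 68%) |

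These counts show opportunity for off-schedule samples. They do not show how often such a sample would differ from the worst scheduled one.

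**3. Tables affected.** Four: 14.3.5.1.2 (hematology), 14.3.5.2.2 (chemistry), 14.3.5.4.2 (coagulation) and 14.3.5.5.2 (complement). Vital signs have no shift table, and 6.2.11 does not name ECG.

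**4. Effect of one affected subject,** 100/n percentage points:

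- n = 6 (target per dose level): 100/6 = 16.7
- n = 9 (maximum of 6 *DNM2* plus 3 *MTM1*): 100/9 = 11.1
- n = 3 (*MTM1* sub-cohort): 100/3 = 33.3
- n = 18 (overall): 100/18 = 5.6

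**5. Chance of at least one affected subject.** This needs a per-subject probability q that the documents do not give. Assuming q, and independence between subjects, the chance is 1 − (1 − q)^n:

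| Assumed q | n = 6 | n = 18 |
|---|---|---|
| 5% | 27% | 60% |
| 10% | 47% | 85% |
| 20% | 74% | 98% |
| 30% | 88% | over 99% |

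**6. CTCAE counts.** Block 14.3.5 of SAP Section 12 has 9 laboratory tables (1.1, 1.2, 2.1, 2.2, 3.1, 4.1, 4.2, 5.1, 5.2), and 0 of 9 apply CTCAE. No such table appears among the struck outputs either. The normal-range shift tables are no replacement: they are per period rather than per time point and carry no grade. Section 10 declares two things only: the added Bayesian analyses, and the cut to IDMC outputs plus selected efficacy parameters.

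**The case against.** **The rules can be read together.** On this view 6.2.11 is the general data rule, and 6.14.2 to 6.14.4 say only how tabulated values are condensed. The SAP's amendment log gives some support: shift tables moved from each visit to the worst result per period because by-visit tables would be too large, not in order to add off-schedule data. Unscheduled samples are also triggered by clinical concern, so their frequency may differ between dose groups. This shows that the wording can be reconciled. It does not remove the consequence, which is that a table described as worst case omits the results most likely to be worst. Uneven ascertainment is a good reason to keep by-visit means on scheduled values, but a weaker one for a worst-result table.

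**The pre-MAD visit is a mild example.** If the last SAD visit is Week 17 (Day 113), adding about 91 days for 3 months gives Day 204, and subtracting 42 days gives Day 162. That is 161 days after a single dose, or 161/21 = 7.7 half-lives at the 21-day value that protocol 1.3.1 reports from a non-human primate study. An abnormality that persists to the scheduled MAD Week 1 Day 1 sample would be tabulated. This stands, and it limits the weight of that example.

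**The consequences are contained.** All laboratory data are listed, the abnormal-value listings 14.3.4.1.1 and 16.2.9.1 are kept, and individual-profile figures are planned, though the SAP does not say whether those plot unscheduled values. Events that qualify reach AE tables 14.3.1.2.6 and 14.3.1.3.1. This stands.

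**Termination and AE grading cover the CTCAE gap.** SAP Section 1 goes on to say that not all planned analyses will be performed, and protocol 7.5.1 requires CTCAE grading for laboratory abnormalities reported as AEs. Neither closes the gap. The table is not among the struck outputs and safety reporting is described as full. Under protocol 7.3, abnormalities judged not clinically significant are not AEs, so AE severity does not capture them.

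**Conclusion.** Both parts hold and should be fixed. As written, the SAP either contradicts itself or produces four worst-case laboratory shift tables that omit off-schedule results. Each affected subject shifts a table by 16.7 points at 6 per dose level, or by 33.3 points in an *MTM1* sub-cohort of 3. These figures use the planned group sizes; the documents do not give the numbers actually enrolled at termination, nor any rate of off-schedule abnormality, so the effect can be stated only per affected subject.

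The CTCAE v5 counts of protocol 9.8 are absent from the SAP and undeclared, and early termination does not explain this.

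The by-visit descriptive tables on scheduled values are sound. The defect is limited to the accuracy and completeness of the by-dose laboratory summaries.

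**What to change.** 1. Reword SAP 6.2.11 along these lines: *By-visit descriptive summaries use scheduled post-baseline values only. Worst-result shift tables use all valid post-baseline results, including repeat and unscheduled ones, and exclude results invalidated for technical reasons.*
2. State which trial period the pre-MAD unscheduled visit belongs to.
3. Add the CTCAE v5 abnormality counts of protocol 9.8 by scheduled time point, with normal ranges where no grading exists, or declare and justify their omission in SAP Section 10. A worst grade per subject is an optional addition.

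**Cost:** SAP wording, four re-programmed shift tables, and either one count table or one paragraph in Section 10. No new data are needed. The worst-case counts may look slightly less favourable.
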